The superscripts associated with each outcome in the “How Answered” boxes in figure 2 refer to the following strategies for testing the hypotheses in Aims 1 and 2: (a) A survey called the Patient Activation Measure (PAM), (Appendix A-1) is completed by patient 1-2 weeks after their visit²²; (b) The “no show rate” is the inverse of Return Visit Adherence (RVA) rate;²³ (c) the Refill rate is “proportion of days covered” (PDC), a metric CMS utilizes in its plan ratings;²⁴ and (d) BP and HgB A1c are checked if they are repeated within 6 months; (e) The SEGUE Framework for evaluating and scoring communication behavior, as rated off of the audio recording by a research assistant utilizing a checklist (Appendix A-2)²⁵ and (f) Content Coding for Contextualization of Care, also called “4C”²⁶. Note: (b-d) are extracted from the CDW and SEGUE and 4C completed while accessing the medical record and listening to the audios. Finally, for all three arms, the members of the research team collecting the data and coding the audio are blinded as to study arm. There is no arm in which the patient is unaware a visit is audio recorded. Blinding the patient is not pertinent to achieving the aims of the study.

Figure 3, the flow diagram below, allocates patients in a parallel three arm randomized controlled trial (RCT) to most efficiently achieve the aims of the study (the calculations for the specific sample sizes are justified later in the protocol – and shown in Tables 4.1 and 4.2. on pp 24+25).

Figure 3: Flow diagram for parallel RCT

Random assignment to arms will be made using computer-generated sequences within the diabetes clinics (1:1 randomization to Arms 1 and 2 in blocks of 4) and primary care clinics (5:5:2 randomization to Arms 1, 2, and 3, in blocks of 24, with one partial block of 8 patients). Solid lines represent unconditional allocation of participants to Arms; dashed lines represent random sampling of participants to create efficient unbiased subsamples for key hypothesis tests. The rationale for the design, starting at the top of the figure and working down, is as follows:

- We start with two separate pools, diabetes and primary care clinics, because measurement of the effect of OAA vs control (Arm 1 vs Arm 2) on Hgb A1c is most efficiently accomplished

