just in the diabetes clinics where every patient has diabetes, many have an A1c>8, and A1c is re-checked at frequent intervals. Hence, analysis of an effect of OAA on diabetes control will occur only in the diabetes clinic population.

- All other measures to achieve Aim 1 will occur in analysis of data collected in both the diabetes and primary care clinics. Hence data on the effect of OAA on show-rates (visit adherence), medication refill rates, blood pressure control etc...will be pooled for patients randomized to Arms 1 and 2 in both the diabetes and primary care clinics.
- The PAM will be applied to the smallest possible subsample of Arms 1 and 2 to test hypothesis 1A (figure 2) with 80% power (Table 4.1, p 24) because it requires a phone call and takes about three minutes of RA and patient time. Subsamples will be drawn at random without replacement by computer. As shown in the Gantt chart (Table 2, p. 18), these calls will be spread out and administered 1-2 weeks post visit (Table 4.0, p 23). This is in contrast to measures of blood pressure, Hgb A1c, and visit and medication adherence, which are extracted from the data warehouse.
- Arm 3, essential to achieve Aim 2, will only occur exclusively in the primary care clinic because it requires blinding physicians to being audio recorded which is not relevant to measuring the effect of OAA on diabetes control, and would confound that measurement.
- Similar to PAM, the SEGUE and 4C analysis require RA time and effort, so will be applied to the smallest possible samples. Whereas PAM is intended to measure the effect of OAA (Arm 1) compared to control (Arm 2) on patient activation, SEGUE and 4C are intended to measure the effect of the physician knowing they are being recorded (Arm 2) versus not knowing (Arm 3) on the process (SEGUE) and content (4C) of the physician's decision making. The SEGUE checklist and the 4C coding occur while the RA is listening to the audio of a visit, randomly sampling 250 audios from the 827 primary care visit audios in Arm 2 for comparison with the 250 audios from Arm 3. Random sampling from Arm 2 primary care visits will be performed by computer without replacement and without regard to whether they are also part of the hypothesis 1A subsample.

Research activities for testing each aim: Anticipating and mitigating risks

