5.2 Recruitment Methods

- State how many subjects will be needed.

The numbers and distribution of patient subjects is presented in Figure 3, above. As noted, a total of 1904 will be recruited from the primary care clinics and 404 from the diabetes clinics, totaling 2308, all above 18 years of age.

The primary subjects are Veterans. However, since providers will be audio recorded as well, and since we will be studying the effect of being audio recorded on the behavior and outcomes of their patients, providers will be considered as human research subjects as well. Since they are not a unit of study, there is no specific sample size.

We also plan to interview hospital leaders about the program. They are also subjects, but given the low risk to them, will likely be exempted from a formal consent process. We anticipate interviewing five leaders at each of the two facilities, for a total of 10.

- Describe when, where, how and by whom potential subjects will be identified and recruited.
- Describe materials that will be used to recruit subjects, e.g., advertisements. Include materials as an appendix or separate attachment.
- Describe any payments to subjects, including the amount, timing (at the end of the study or pro-rated for partial study participation), method (e.g., cash, check, gift card), and whether subjects will experience a delay in receiving the payment.

Recruitment will proceed as follows:

(A) Providers (physicians or nurse practitioners) will be notified of the project by the site investigator by attending their section meetings (at the invitation of the section chiefs — who have already indicated support of the project) and providing a brief description and study brochure (same as the one shared with patients). Those who wish to participate will sign a sheet providing their name and contact information. In addition, the PI will send out an email to providers who were not able to attend the meeting. The site investigator and/or RA will meet with all who indicate interest to complete the informed consent process.

NOTE: When clinical section meetings are held virtually because of the COVID-19 pandemic, these activities will also be conducted virtually. Handouts and sign-up sheets will be emailed.

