Recruitment of providers for focus group participation will occur via email invitation, and is optional for all participating providers. Providers are first informed of the focus groups in during the informed consent process for the study, as detailed in the consent document. They are informed that they will be contacted about participation, that participation will be voluntary, that the focus groups will be audio recorded, and that to minimize risk, they will be asked not to use their names or the names of any patients during the focus groups. They are also informed that lunch

will be served. The email text is provided with this protocol and informs providers that "if you are interested, please reply to this message."

(B) Recruitment of patients will occur in primary care and diabetes clinics in Chicago (Jesse Brown) and Cleveland (Louis Stokes). Since the former is nearly three times larger than the latter, it is anticipated that recruitment will be proportional. However, it will continue at both site until target numbers are achieved. The method of recruitment is as follows:

In primary care, the research team will obtain the panel lists of all participating providers. These are accessed through CPRS under each providers schedule. They will then randomly select the subset of patients necessary to contact via mail 2-4 weeks prior to their scheduled appointments informing them of the study and explaining how to opt out. Based on a 2014-16 study we conducted involving audio recording visits (SDR 12-280) we plan to mail 2767 prospective subjects, taking into account that 20% opt out, decline during the outreach call, are not reachable, don't show up in clinic, or opt out on site. About a week prior to the visit the RA will then phone those who do not opt out, to achieve recruitment of 1904 patients to be distributed across 2 sites (Chicago and Cleveland) and divided by randomization, utilizing the computer-generated sequences detailed in the research to allocate 827, 827, and 250 subjects to Arms 1, 2, and 3 respectively. Those who are reached and affirm will agree to arrive approximately 20 minutes early for their appointment.

For the diabetes clinic patients, an additional 404 patients will be randomly assigned to Arms 1 and 2. The same opt out strategy described above for primary care will be employed to recruit patients to these clinics as well.

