5.5 Study Evaluations

- Describe all evaluations to be conducted (including screening; tests/questionnaires that will be administered; any procedures that subjects will be required to complete) and data collection methods. Include materials as an appendix or separate attachment.

There will be several sources of research material. Instruments are included in appendices A-1 through A-8 as indicated below and as attached:

- A) Audio recordings of encounters made with written consent by both patients and providers. The audios are collected for research purposes.
- B) The patient's medical record: Following a 10% (n=250) random sample of audio recorded visits (arm 3), again with written patient subject consent, a trained coder will extract discrete pre-determined variables for "4C" coding from the medical record after the visit, based on the referenced 4C manual.
- C) Phone calls to a random (40%) sample of patients to complete the Patient Activation Measure.
- C) Surveys of all patients (a brief literacy screen), and of both patients (25% of encounters) and all providers about their experience participating in an OAA program. (for patients: A-1, A-7, A-8; for providers: A-2, A-3).
- D) Provider focus groups about their experience participating in an OAA program. (A-4, A-5)
- E) Structured interviews with facility leaders about their experiences with the OAA program. (A-6)

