As noted earlier, the PAM will be completed over the phone by the RA initially at one week after the visit (this will be extended to 10-14 days if it turns out a substantial number of patients listen to the audio more than one week after the visit).

Table 4.1 lists the calculated power for the intention-to-treat analyses for Hypotheses 1A-1C by outcome. These analyses are based on data from 1029 combined primary care and diabetes clinic visits each in Arms 1 and 2 (i.e. sample size 2058), except for measuring the effect of OAA on Hgb A1c (in 1C) which is based only on 202 diabetes clinic visits each in Arms 1 and 2 (total 404). For patient activation (1A), we assume veterans with no audio access will have a mean PAM score of 56 and standard deviation of 19.5, based on a 2016 national study of VA health care users;³⁵ clinically meaningful differences in activation have been described as 4-6 points.³⁶ Since testing hypothesis 1A requires a phone call to administer the PAM, we will randomly contact 924 participating subjects, an average of 9 calls/week across sites, which will achieve 80% power, instead of calling all 2058 subjects. Baseline rates of each undesirable outcome for 1B are derived from our previously published study in the VA using recordings without provider awareness or patient access (as in Arm 3), and we expect to find an odds ratio of 0.5 for each outcome when patients have access to audios.¹⁴ Baseline rates of each undesirable outcome for 1C are derived from the data warehouse (Chicago and Cleveland facilities – see table 3, above).

Table 4.1: Expected differences and power for planned intention-to-treat analyses for hypothesis 1A-1C

Hypothesis	Outcome	Baseline without audio available	Expected with audio available	Sample size	Power

		(Arm 2)	(Arm 1)	(total)	
1A	Patient activation (PAM 0-100 score)	56.0	60.0	924	80%
1B	Visit no-show rate	7%	4%	2058	95%
	Medication Proportion of days not covered	13%	7%	2058	80%
1C	Hgb A1c > 8 with repeat in < 6 Mo	66-70%	33-35%	404	80%
	Most Recent SBP>140 or DBP>90* with repeat in < 6 Mo	39%	24%	2058	99%

Also, while not included in Table 4.1, because it is not a primary objective of Aim 1, we will explore whether OAA is associated with fewer ED visits and hospitalizations. With the current sample size, we will in fact have 80% power to detect a decrease in inpatient admissions from 14%, the 2018 rate in our study population, to 9%.

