Table 4.2 lists the calculated power for the analyses for Hypothesis 2A and 2B (comparisons of Arm 2 vs. Arm 3) based on actual Veteran visits by outcome. Baseline SEGUE scores are based on SEGUE's validation study among general internists (mean 17.5, sd 1.77); that study found that medical students in a skills lab achieved mean SEGUE scores of 21.1 (sd 2.1), and we take that as our minimal expected level of improvement from knowledge that one is being observed. Baseline rates of contextual probing and planning are based on our prior study in the VA using recordings without provider awareness or patient access (as in Arm 3), and incorporate the expectation that contextual red flags suitable for probing will be present in 2/3 of encounters and contextual factors that should be incorporated in planning will be present in 1/4 of encounters overall.¹⁴ Expected increases in probing and planning are based on odds ratios from our prior study comparing these measures in undercover visits to providers with the same cases presented to medical students in a testing setting (and are thus conservative measures of how much better providers would likely perform if they were aware vs. unaware they were being tested).¹³ To obtain at least 80% power for each of these comparisons, we will randomly sample 250 primary care clinic visits (from 827 Arm 2 primary care visits), and enroll all 250 primary care visits in Arm 3 for the SEGUE and 4C coding processes. For 4C, we expect 168 visits/arm with red flags suitable for probing and 63 visits/arm with contextual factors suitable for planning.

Table 4.2: Expected differences and power for planned analyses for hypotheses 2A and 2B

Outcome	Baseline (doctor unaware, n=250)	Expected (doctor aware, n=250)	Sample size (total)	Power
SEGUE provider score	17.5	21	500	99%
Contextual probing rate ^{13,26}	32%	47%	500	80%
Contextual	59%	82%	500	82%

planning rate ^{13,26}				
--------------------------------	--	--	--	--

All effects measured in Aim 1 and 2 will be adjusted for patient sociodemographic characteristics which will be obtained from the CDW (including age, gender, and race) or from administering the REALM-SF to assess literacy. Internet access, for those in the intervention arm, will be ascertained by census track using geocoding of patient addresses, based on FCC data, a method developed by Perzynski et al.^{37,38}

Aim 3:

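### 5:5:2 randomization in blocks of 24 yields about 793/793/317 primary care patients, not the stated 827/827/250

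*Combined protocol and SAP*

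**What the plan says.** The text under Figure 3 in section 5.1 sets the primary care allocation: "5:5:2 randomization to Arms 1, 2, and 3, in blocks of 24, with one partial block of 8 patients". Diabetes clinic patients are randomized separately, 1:1 to Arms 1 and 2.

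Section 5.2 gives the totals: "a total of 1904 will be recruited from the primary care clinics and 404 from the diabetes clinics, totaling 2308". For primary care it says the computer-generated sequences will be used "to allocate 827, 827, and 250 subjects to Arms 1, 2, and 3 respectively", and it describes the 404 diabetes patients as additional.

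The arm sizes recur elsewhere:

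- Section 5.1, on SEGUE and 4C coding: "randomly sampling 250 audios from the 827 primary care visit audios in Arm 2 for comparison with the 250 audios from Arm 3".
- Section 5.5 puts Arm 3 at 10% of recorded visits, n=250.
- Section 5.6, before Table 4.2: "enroll all 250 primary care visits in Arm 3 for the SEGUE and 4C coding processes".
- Section 5.6, before Table 4.1, bases Aim 1 on 1029 visits per arm (827 + 202), 2058 in total.

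**The concern.** A randomization ratio with a block size is an instruction that a programmer carries out. Together with the total it fixes the arm sizes to within a few patients. Here they differ from the stated sizes by far more than a partial block can absorb, and no section says which figure governs.

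If the ratio governs, Arm 3 grows by about 67 patients, each concealing a recorder from the provider. Coding all of Arm 3, as section 5.6 says, then means about 317 audios, although section 5.1 explains that "the SEGUE and 4C analysis require RA time and effort, so will be applied to the smallest possible samples". The Aim 1 sample size in Table 4.1 also becomes wrong.

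If the targets govern, the stated sequence cannot produce them. One way to reach 250 would be to close Arm 3 partway through recruitment. The documents do not say this will happen. If it did, part of the Arm 2 sample used for Aim 2 would have no concurrent Arm 3 comparator.

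**Working it through.** **Inputs.** Ratio 5:5:2, block size 24 and partial block of 8 (section 5.1). Primary care total 1904, diabetes total 404 and arm sizes 827/827/250 (section 5.2). Aim 1 size 1029 per arm and the outcome rates (section 5.6, Tables 4.1 and 4.2).

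**The plan's own sums.** 827 + 827 + 250 = 1904. 1904 + 404 = 2308. 827 + 202 = 1029, and 2 × 1029 = 2058. The stated sizes agree with one another. The ratio is what does not fit.

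**What the ratio gives.**

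- 1904 = 79 × 24 + 8, so the stated block size and partial block match this total exactly.
- One block of 24 at 5:5:2 is 10/10/4. Seventy-nine blocks give 790/790/316.
- The last 8 patients add 0 to 8 to Arm 1, 0 to 8 to Arm 2 and 0 to 4 to Arm 3.
- The expected sizes are 1904 × 5/12 = 793.3 in each of Arms 1 and 2, and 1904 × 2/12 = 317.3 in Arm 3.

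| | Stated | From 5:5:2 | Range | Difference |
|---|---|---|---|---|
| Arm 1, primary care | 827 | 793 | 790–798 | −4% |
| Arm 2, primary care | 827 | 793 | 790–798 | −4% |
| Arm 3 | 250 | 317 | 316–320 | +27% |
| Arms 1 + 2 with diabetes | 2058 | 1991 | – | −3.3% |

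The pooled figure is 2 × 793.3 + 404 = 1990.7, about 995 per arm. Arm 3 would be 317/2308 = 13.7% of all visits, against 250/2308 = 10.8%. Chance does not explain the gap: under simple unblocked 5:5:2 randomization, 250 lies (250 − 317.3)/√(1904 × 1/6 × 5/6) = −4.1 standard deviations from expectation.

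**Effect on power** (z test for two proportions with pooled variance, two-sided 0.05, no clustering; the last two are assumptions).

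| Outcome | 1029 per arm | 995 per arm |
|---|---|---|
| No-show, 7% vs 4% | 84.8% | 83.6% |
| No-show, 7% vs 3.63% (odds ratio 0.5) | 92.7% | 91.9% |
| Days not covered, 13% vs 7%, treated as a proportion | 99.5% | 99.4% |
| Blood pressure, 39% vs 24% | above 99% | above 99% |

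These baselines are not all those of Table 4.1, which states 95% for no-shows and 80% for days not covered. What matters here is the change between columns. The PAM (924) and A1c (404) rows do not depend on the primary care split.

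For Aim 2, coding about 317 Arm 3 audios against 250 from Arm 2 would raise power from about 81% to 85% for probing (32% vs 47%, two thirds of visits). For planning (59% vs 82%, one quarter of visits) it would rise from about 82% to 85%.

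**If Arm 3 were closed at 250 (not stated anywhere).** Sixty-two blocks hold 248 Arm 3 places (1488 patients), so the 250th falls in block 63, at about patient 1500. That leaves 1904 − 1500 = 404 primary care patients, 202 of them in Arm 2. Then 202/827 = 24.4% of Arm 2, or about 61 of the 250 sampled for coding, would have no concurrent Arm 3 patient.

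**A possible source of the mismatch.** With 250 in Arm 3, 5:5:2 gives 625/625/250, or 1500 patients. Adding 202 diabetes patients to each of Arms 1 and 2 gives exactly 827/827/250 = 1904. So 1904 might already contain the 404. Against this, section 5.2 counts the 404 separately, and 1500 = 62 × 24 + 12 would leave a partial block of 12, not 8. If it were so, Aim 1 would have 827 per arm (1654 in total), and power for 7% vs 4% would be 76.3%.

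**The case against.** The strongest reply is that little depends on this. Arms 1 and 2 stay 1:1, the 250 per arm in Table 4.2 can still be met, and Aim 1 loses about one point of power. A random 250 could be drawn from a larger Arm 3, as is already done in Arm 2. Because 250 and 827 recur in several sections, the ratio in section 5.1 may simply be the misprint. All of this is fair on weight, but it does not remove the contradiction. Nor can 250 be read as a subsample of a larger arm: section 5.2 allocates 250, and section 5.6 takes all of Arm 3.

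Early closure is indeed hypothetical, and the same identity (625 + 202 = 827) fits a double count of the diabetes patients equally well. The partial block of 8 is not decisive against a double count, since it could have been computed from an already mistaken 1904. Section 5.2 does count the 404 separately, so a double count is unproven. But if it occurred, changing only the ratio or the arm sizes would leave the wrong total in place. This part of the objection stands, and it is why the totals should be confirmed first.

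**Conclusion.** The concern holds. The 5:5:2 scheme in blocks of 24 with a partial block of 8 fits the 1904 primary care patients exactly and cannot give 827/827/250, whatever the order within the partial block. Following the ratio puts about 67 more patients than stated in Arm 3 and about 34 fewer in each of Arms 1 and 2, and lowers the pooled Aim 1 sample from 2058 to about 1991.

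The arm sizes rest only on the protocol's own figures. The power changes assume a two-sided 5% test and no clustering by provider. They are about one percentage point for no-shows and negligible for the other Aim 1 outcomes. This should be fixed because the allocation rule cannot be carried out as written, not because the trial's conclusions are threatened. The early-closure and double-count readings are possibilities to rule out, not findings.

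**What to change.** First confirm that the 404 diabetes patients are not already inside 1904, so that 1904, 2058 and 2308 are all sound. Then make the ratio, block size and targets agree before the list is generated. If a list is already in use, state which scheme produced it and correct the other figures.

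- **Option (a): keep 5:5:2.** Restate the primary care arms as about 793/793/317 and the pooled size as about 1991 in Figure 3, sections 5.1, 5.2, 5.5 and 5.6, and Table 4.1. Say whether all Arm 3 audios or a random 250 will be coded. The cost is text edits, plus up to about 67 more audios if all are coded.
- **Option (b): keep 827/827/250.** Replace 5:5:2 with another scheme. One example is a randomly ordered mix of 58 blocks of 23 (10/10/3) and 19 blocks of 30 (13/13/4): 58 × 23 + 19 × 30 = 1904, Arms 1 and 2 at 580 + 247 = 827 each, Arm 3 at 174 + 76 = 250. There is no partial block, and Arm 3 stays open throughout. The exact totals need a single list that is completed; separate site lists could end mid-block. The cost is one corrected sentence and a regenerated list.

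Either way, state that Arm 3 is not closed early. Neither option needs extra patients if 1904 is right. If the 404 prove to be double-counted, the Aim 1 sample size and power must be reworked as well.

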As summarized in Table 4, we will apply several measures to assess the effectiveness of the intervention, testing hypotheses to achieve Aims 1 and 2. For each hypothesis, comparisons between arms will be made using mixed-effect linear or logistic regression as appropriate for the outcome, with a fixed effect of study arm, VA site, and primary vs. secondary care setting, and a random effect of provider to accommodate clustering of visits within providers. Of primary interest is the direction, magnitude, and significance of the regression coefficient associated with study arm. Primary analysis will compare arms on an intention-to-treat basis, without regard to whether audio made available in Arm 1 is actually accessed by anyone; secondary analyses will include covariates representing whether, how often, and by whom (patient or provider) audio is actually accessed in Arm 1 to assess the impact of audio use (vs. availability). As patients will be randomized to arms, we do not expect demographic or other patient differences among arms, but will conduct tests for differences, and if any variables differ significantly among arms, we will include them as covariates in the regression models.

Table 4. Hypotheses and evaluation strategy for effectiveness of intervention (Aims 1 and 2)

Hypothesis	Evaluation Strategy
1A: OAA increases patient activation.	Administer PAM (Appendix A-1) 1-2 weeks post visit via phone call and compare scores in Arm 1 vs. Arm 2
1B: OAA increases care plan adherence, including fewer no-shows and more on-time refills.	Utilizing the data warehouse measure Return Visit Adherence (RVA) and refill rates (PDC) ^{24,32,33} in Arms 1 vs. 2.
1C: OAA reduces Hgb A1c and BP	Same as above: Utilizing data warehouse measure A1c and BP.
2A: Providers obtain higher scores on measures of communication behavior when they know they are being recorded.	Completed by trained RA off of Audio: SEGUE checklist for communication completed by research team (Appendix A-2) ²⁵ , comparing randomly sampled visits in Arm 2 vs Arm 3.
2B: Providers obtain higher scores on measures of attention to patient contextual factors essential to care planning when they know they are being recorded.	4C for contextualization of care ³⁴ , comparing randomly sampled visits in Arm 2 vs Arm 3.

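### Matching the 250 Arm 2 audios coded for Aim 2 to each provider's Arm 3 count would give a small gain in precision for no extra coding; the planned simple draw is unbiased

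*Combined protocol and SAP*

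**What the plan says.** Section 5.1 (Study Design, rationale for Figure 3) limits SEGUE and 4C coding to the smallest workable samples, because it takes research assistant time. It specifies "randomly sampling 250 audios from the 827 primary care visit audios in Arm 2 for comparison with the 250 audios from Arm 3". Section 5.6 repeats the draw above Table 4.2: "we will randomly sample 250 primary care clinic visits (from 827 Arm 2 primary care visits".

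On how the draw is made, Section 5.1 says: "Random sampling from Arm 2 primary care visits will be performed by computer without replacement". The only qualifier it adds is that overlap with the subsample used for hypothesis 1A plays no part. Provider is not mentioned.

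Randomisation is by clinic type, with "primary care clinics (5:5:2 randomization to Arms 1, 2, and 3, in blocks of 24, with one partial block of 8 patients"; no stratification by provider is stated. For every hypothesis, Section 5.6 fits a mixed linear or logistic model with fixed effects of arm, site and care setting and "a random effect of provider to accommodate clustering of visits within providers". On the number of providers, Section 5.2 says: "Since they are not a unit of study, there is no specific sample size".

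**The concern.** SEGUE and 4C both score what the provider does, so visits to the same provider may resemble each other. A model with a provider effect then draws much of its information on awareness of recording from providers who have coded visits in both arms. Under a simple draw, one provider's Arm 3 visits may be set against many coded Arm 2 visits and another's against few or none. The unpaired visits still cost coding time but add less to the comparison.

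With 827 Arm 2 visits to choose from and only 250 needed, near 1:1 matching within provider should be possible. Section 5.1 asks for subsamples that are both unbiased and efficient. The simple draw meets the first aim and falls a little short of the second. What is at stake is a modest amount of precision, chiefly of interest for the two 4C outcomes, which Table 4.2 plans at 80% and 82% power.

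**Working it through.** **Inputs from the documents.** Primary care allocation 827/827/250 (Section 5.2); 250 coded visits per arm; SEGUE 17.5 versus 21, SD 1.77 (2.1 in the skills-lab students); probing 32% versus 47% on 168 usable visits per arm; planning 59% versus 82% on 63 per arm (Section 5.6 and Table 4.2).

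**Assumed, because not stated.** Two-sided alpha 0.05; 20, 40 or 80 providers with equal or unequal visit volume (coefficient of variation 0 or 0.7); provider ICC 0.01 to 0.30.

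**Step 1: reproduce Table 4.2, treating visits as independent.**

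- SEGUE: SE = 1.77 × √(2/250) = 0.158, and 3.5/0.158 ≈ 22. With SD 2.1, 3.5/0.188 ≈ 19. Power is essentially 100% (stated 99%).
- Probing: mean rate 0.395. Null SE = √(2 × 0.395 × 0.605/168) = 0.0533; alternative SE = √((0.32 × 0.68 + 0.47 × 0.53)/168) = 0.0527. z = (0.15 − 1.96 × 0.0533)/0.0527 = 0.86, power 80.6% (stated 80%).
- Planning: mean rate 0.705. Null SE = √(2 × 0.705 × 0.295/63) = 0.0813; alternative SE = √((0.59 × 0.41 + 0.82 × 0.18)/63) = 0.0786. z = (0.23 − 1.96 × 0.0813)/0.0786 = 0.90, power 81.6% (stated 82%).

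The stated figures reproduce.

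**Step 2: what matching does.** Take total variance 1 and a random provider intercept with ICC ρ. Provider j, with a coded Arm 2 visits and b coded Arm 3 visits, contributes ab/(a+b) to the within-provider information. If a = b for every provider, the sum is 250/2 = 125 and the variance of the arm effect is (1 − ρ)/125 = 2(1 − ρ)/250, the smallest available from 250 + 250 visits.

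Under the simple draw, simulation (300 trials per setting) puts about 36 to 78 of the 250 Arm 2 visits outside the provider match. Within-provider information is 84% to 96% of the maximum. If only that information counted, the variance ratio of simple to matched draw would be 1/0.96 = 1.04 to 1/0.84 = 1.19. The random-intercept model also recovers between-provider information, so the true ratio is lower and approaches 1 as ρ falls.

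Worked case for SEGUE, 40 equal-volume providers, ρ = 0.10: matched variance 2 × 0.90/250 = 0.0072. The simulated ratio is 1.049, so the simple draw gives 0.0072 × 1.049 = 0.00755, and the SE is √1.049 = 1.024 times as large.

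**Step 3: 4C outcomes.** Visits were thinned at random to 2/3 (probing) and 1/4 (planning), because red flags and contextual factors are known only after coding. Power comes from the effective sample size and the two-proportion formula of Step 1. Selected equal-volume settings:

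| Providers, ICC | Outcome | Variance ratio | Power, simple | Power, matched |
|---|---|---|---|---|
| 40, 0.01 | Probing | 1.007 | 80.0% | 80.3% |
| 40, 0.01 | Planning | 1.006 | 80.2% | 80.4% |
| 40, 0.10 | Probing | 1.037 | 82.0% | 83.3% |
| 40, 0.10 | Planning | 1.023 | 81.3% | 82.1% |
| 80, 0.30 | Probing | 1.113 | 87.5% | 90.7% |
| 80, 0.30 | Planning | 1.064 | 85.0% | 87.1% |

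**Step 4: range.** Over 20 to 80 providers and ICC 0.02 to 0.30, the variance ratio is 1.01-1.12 for SEGUE, 1.01-1.11 for probing and about 1.00-1.07 for planning. A separate set of runs over ICC 0.01 to 0.30 agreed to within 0.01 at the upper ends.

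**Step 5: feasibility.** On average 0 to 4 of the 250 could not be matched for want of Arm 2 visits with the same provider.

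**The case against.** The strongest reply is that nothing is wrong. A simple random draw is unbiased, and the model already has a provider effect and a site effect, so chance imbalance in either is largely dealt with at analysis. That stands, and it is why the point is only a refinement. It is also true that the plan never says provider is disregarded: its phrase about sampling without regard to something concerns the hypothesis 1A subsample. The absence of provider matching is inferred from the plan's silence in Sections 5.1, 5.2 and 5.6.

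Three stronger readings are tempting, and the documents support none of them.

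- A reader might infer that the 4C comparisons are at risk because they are planned at only 80% and 82%. In every setting tried, the simple draw kept power at or above 80%.
- A reader might infer that matching helps 4C most. The proportional gain is smallest for planning, because matching all visits only roughly matches the visits that turn out to be usable. SEGUE gains at least as much but does not need it.
- A reader might turn the gain into dozens of extra audios: 12% of 500 would be 60. That is the top of the SEGUE range, where power is already about 100%, and it needs many providers and a high ICC. The documents give neither figure.

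**Conclusion.** The point holds as an optional efficiency refinement. The simple draw is valid. A provider-matched draw is more precise for the same 500 coded audios: the variance of the arm effect is otherwise about 1-12% larger for SEGUE, 1-11% for probing and 0-7% for planning. That is an SE up to about 6% larger (√1.12 = 1.058) and roughly 0 to 3 points of power for 4C.

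The direction follows from the model. The size rests on assumed provider numbers and ICC, a random intercept only, and a linear-scale approximation for the two binary outcomes. At low ICC there is almost nothing to gain.

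One related inconsistency affects how the fix is worded. Applying 5:5:2 to 1904 gives 1904 × 2/12 ≈ 317 in Arm 3 and 1904 × 5/12 ≈ 793 in each of Arms 1 and 2, whereas Section 5.2 plans to "allocate 827, 827, and 250 subjects to Arms 1, 2, and 3 respectively". The two statements need reconciling. The conflict does not change the direction of the result, but tying the Arm 2 draw to whatever Arm 3 total accrues could add about 317 − 250 = 67 audios. The Arm 2 total should therefore stay fixed at 250.

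**What to change.** Replace the sampling sentence in Section 5.1, and refer to it from the text above Table 4.2 in Section 5.6:

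> The 250 Arm 2 primary care audios will be drawn by computer at random without replacement within provider, in numbers matched to each provider's Arm 3 visits (in proportion, if Arm 3 does not close at 250). Where a provider has too few Arm 2 visits, the shortfall is drawn at random from other providers at the same site. The total remains 250.

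Keep the existing statement that membership of the hypothesis 1A subsample plays no part. Add that the draw is made after Arm 3 accrual is complete, or in batches alongside it, since each provider's Arm 3 count must be known first.

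The cost is a few lines in the sampling program and attention to timing. Section 5.1 already assigns a provider code to each audio. The draw uses only provider and site, so it adds no bias and no coding. The program does the matching, so coders remain blind to arm.
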